### Questions about your health and work

Researchers call this questionnaire the iMTA PCQ (iPCQ).

#### Explanatory notes

##### **Please read this first!**

##### **Are you unable to complete the questionnaire yourself?**

If you are unable to complete the questionnaire yourself, perhaps someone can help you. A member of your family, for example.

##### **What is the questionnaire about?**

The questionnaire is about your health and work in the past 4 weeks.

##### **How long does it take to complete the questionnaire?**

It takes roughly 10 minutes to complete the questionnaire.

##### **How should you complete the questionnaire?**

- Start with the first question and follow the numbering.
- .
- For some questions, you can enter a number or something else on the dotted line.
- There are no wrong answers.

**What will happen with your answers?**

Your answers will be used for research. Only the researchers will see your answers. So nobody else will.

The researchers will not write down your name anywhere. And they will not tell anyone that you have taken part in the trial.

**It is great that you want to complete the questionnaire for us!**

**Question 1. What do you do in daily life?** Check the box for what best describes your primary occupation.

- I am at school, I study
- I am in paid employment
- I am self-employed
- I am a housewife/househusband
- I am unemployed
- I am disabled for working, for, ... % (bodily percentage)
- I am retired or have taken early retirement
- I do something else, namely .....

**Question 2. Do you have paid work?**

- No
- Yes

You will first have questions about your job. So, about work for which you are paid. *Do you not have a paid job*? Then continue with question 12. First, read the explanatory notes above question 12.

**Question 3. What is your occupation?**

.....

**Question 4. How many hours a week do you work?** Add together all the hours for which you are paid.

..... hours

**Question 5. How many days a week do you work?**

..... days

**Question 6. Have you been absent from your work in the past 4 weeks because you were ill?**

- No
- Yes, I was absent for..... days

*(Only count the working days in the past 4 weeks)*

Have you checked the "Yes" box? Then answer question 7.

Otherwise continue with question 9.

**Question 7. Have you been absent from your work because of being ill for longer than the entire period of 4 weeks?** This refers to an uninterrupted period of absence from work.

No

Yes

Have you checked the “Yes” box? Then answer question 8. Otherwise continue from question 9.

**Question 8. When did you report being ill?**

Day/month/year: ...../...../..... Continue with question 12. *First, read the explanatory notes above question 12.*

**Question 9. Have there been days over the past 4 weeks when you worked but suffered from physical or psychological problems during your work?**

No

Yes

Have you checked the “Yes” box? Then answer questions 10 and 11.

Otherwise continue with question 12. *First, read the explanatory notes above question 12.*

**Question 10. On how many working days have you suffered from physical or psychological problems during your work?** Just count the working days over the past 4 weeks.

..... working days

**Question 11. On the days when you were suffering from problems, perhaps you were not able to do as much work as normal. On those days, how much work could you do on average?** Look at the numbers below. A 10 means that you were able to do just as much as normal on those days. A 0 means that you were not able to do anything on those days. Circle the right number.

I was not able to do just as much as normal  
I could do around half  
I was able to do anything to do just as much as normal

0 1 2 3 4 5 6 7 8 9 10

**Explanatory notes to question 12**

You may also suffer from your physical or psychological problems during unpaid work. Sometimes you can do less as a result. For example, you cannot care properly for the children or do volunteer work. Or you may not be able to do the shopping or do gardening. That is what the next questions are about.

**Question 12. Have there been any days on which you were able to do less unpaid work because of your physical or psychological problems?** This relates to days over the past 4 weeks.

No

Yes

Have you checked the “Yes” box? Then answer questions 13 and 14. Otherwise, this was the last question..

**Question 13. On how many days was this the case?** Only count the days in the past 4 weeks.

.... days

**Question 14. Suppose that someone, for example your partner, a family member or an acquaintance, has helped you on these days. And did all that unpaid work for you, that you could not do. How many hours, on average, was that person busy with it on these days?**

On average ..... hours on these days

**That was the last question.**

**Have you got any questions or comments?**

Perhaps you have some more questions or comments? If so, please enter them below.

.....  
.....  
.....

**Thank you very much!**

## Questionnaire sur votre santé et votre travail

Les chercheurs appellent ce questionnaire l'iMTA PCQ (iPCQ).

### Explication

**Veillez lire ceci avant de compléter le questionnaire.**

#### **Vous ne pouvez pas remplir le formulaire tout(e) seul(e) ?**

Si vous n'êtes pas en mesure de compléter le formulaire tout(e) seul(e), quelqu'un peut peut-être vous aider, un membre de votre famille par exemple.

#### **Sur quoi ce questionnaire porte-t-il ?**

Ce questionnaire porte sur votre santé et votre travail au cours des quatre dernières semaines.

#### **Combien de temps cela prend-il de remplir le formulaire ?**

Compléter le formulaire prend environ 10 minutes.

#### **Comment devez-vous remplir le formulaire ?**

- Commencez par la première question puis suivez la numérotation.
- 
- Pour certaines questions, vous pouvez écrire un nombre ou répondre sur les pointillés.
- Il n'y a pas de mauvaises réponses.

#### **Qu'advient-il de vos réponses ?**

Vos réponses serviront à la recherche. Seuls les chercheurs verront vos réponses. Cela veut donc dire que personne d'autre n'y aura accès.

Les chercheurs n'écriront votre nom nulle part. Et ils ne diront à personne que vous avez participé à ce projet de recherche.

**Nous vous sommes très reconnaissants de bien vouloir compléter ce formulaire pour nous !**

**Question 1. Quelle est votre occupation ?** Inscrivez une **x** dans la case correspondant à votre activité habituelle.

- Je vais à l'école, je suis étudiant(e)
- Je suis salarié(e)
- Je suis travailleur/se indépendant(e)
- Je suis femme/homme au foyer
- Je suis demandeur/se d'emploi
- Je suis en incapacité de travail à hauteur de .... %
- Je suis à la retraite ou bénéficie d'une retraite anticipée
- J'ai une autre occupation, à savoir.....

**Question 2. Avez-vous un emploi rémunéré ?**

- Non
- Oui

Les questions suivantes portent sur votre travail. C'est-à-dire, un emploi pour lequel vous êtes rémunéré(e). Vous n'avez pas d'emploi rémunéré ? Passez à la question 12. Veuillez d'abord lire l'explication précédant la question.

**Question 3. Quel est votre profession ?**

.....

**Question 4. Combien d'heures par semaine travaillez-vous ?** Comptez uniquement les heures rémunérées.

..... heures

**Question 5. Combien de jours par semaine travaillez-vous ?**

..... jours

**Question 6. Vous êtes-vous absenté(e) de votre travail au cours des 4 dernières semaines pour raison de santé ?**

- Non
- Oui, je me suis absenté(e) ..... jours.

(Comptez uniquement les jours d'arrêt de travail au cours des 4 dernières semaines.)

Vous avez répondu « Oui » ? Passez à la question 7.  
Sinon, passez à la question 9.

**Question 7. Vous êtes-vous absenté(e) de votre travail avant la période des 4 semaines pour raison de santé ?** Cela concerne une période ininterrompue complète d'arrêt de travail à cause d'une maladie.

- Non  
 Oui

Vous avez répondu « Oui » ? Passez à la question 8.  
Sinon, passez à la question 9.

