**Vraag 6. Bent u in de afgelopen 4 weken afwezig geweest van uw werk omdat u ziek was?**

- Nee
- Ja, ik ben ..... dagen afwezig geweest

(Tel alleen de werkdagen in de afgelopen 4 weken)

Heeft u "Ja" geantwoord? Beantwoord dan vraag 7.

Ga anders verder met vraag 9.

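### French iPCQ question 7 asks about absence before the last 4 weeks, not absence lasting longer than the whole 4 weeks, so some employed French-speaking patients can be routed past the reduced-work questions

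*Protocol*

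**What the plan says.** Sections 8.1.2 and 10.5 of the protocol use the iPCQ, sent at 90 days, to measure productivity loss for the cost-effectiveness analysis, which belongs to the tertiary objective in section 2. Section 17 gives the form in Dutch, English and French, and section 12.2 refers to French-speaking centers.

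Question 6 asks about sick absence in the past 4 weeks and the number of days. A yes leads to question 7.

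- English question 7: "Have you been absent from your work because of being ill for longer than the entire period of 4 weeks", followed by "This refers to an uninterrupted period of absence from work".
- French question 7: whether the patient was "absenté(e) de votre travail avant la période des 4 semaines pour raison de santé", followed by "Cela concerne une période ininterrompue complète d'arrêt de travail à cause d'une maladie".

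The routing is the same in both. A yes at question 7 leads to question 8, which asks for the date the leave began, and then to question 12. A no leads to question 9. Questions 9 to 11 ask about days worked with health problems and how much work was still possible.

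The counting note at question 6 also differs. English says "Only count the working days in the past 4 weeks" and Dutch says "Tel alleen de werkdagen in de afgelopen 4 weken". French counts days of "arrêt de travail au cours des 4 dernières semaines".

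**The concern.** Question 7 decides which data are collected. Skipping questions 9 to 11 loses nothing only if the patient did no work in the 4-week window. The English wording aims at such patients: it refers back to the 4-week period and asks for an unbroken absence longer than all of it. The French wording asks about the time before the window. With a form sent at 90 days, the window runs from about day 62 (90 − 28) to day 90 after an acute stroke, so a patient may well have been on leave before it and yet have worked during it.

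What is at stake is a productivity measure collected by different rules in different languages. A misrouted patient looks like someone on leave since the date given at question 8, and the answers on reduced output are never asked for. An analysis plan can set how the recorded date is costed, but it cannot recover unasked answers.

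**Working it through.** The protocol states no figure to reproduce here, so the check is a trace of the skip logic. It assumes that the form is completed at day 90 and that the English question means an absence covering the whole window and more. For French there are two readings: the opening question taken alone, or the limiting sentence applied to the patient's current leave.

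| Patient | English Q7 | French Q7, opening question alone | French Q7, limiting sentence applied to current leave |
|---|---|---|---|
| A. Off work since the stroke without a break | Yes: Q8, Q12 | Yes: Q8, Q12 | Yes: Q8, Q12 |
| B. Off after the stroke, back before day 62, separate sick day later | No: Q9–11 | Yes: Q8, Q12 | No: Q9–11 |
| C. Leave began before day 62 and ended inside the window, then back at work | No: Q9–11 | Yes: Q8, Q12 | Yes: Q8, Q12 |
| D. Back at work, no sick day in the window | Q7 not reached | Q7 not reached | Q7 not reached |

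The versions agree for A and D. They diverge for C on either French reading. For B they diverge only if the limiting sentence is not tied to the current leave, and nothing in it makes that tie: it says the leave was unbroken, not that it continued into the window.

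**Illustration of the possible overstatement (assumed patient).** Five-day worker, back at work on day 50, 2 sick days in the last 4 weeks, who answers yes at French question 7 and enters the stroke date at question 8.

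- Actual absence over 90 days: 50 × 5/7 + 2 = 35.7 + 2 = 37.7, about 38 working days.
- If leave were costed from the question 8 date through day 90: 90 × 5/7 = 64.3, about 64 working days.
- Overstatement under that rule: 64.3 − 37.7 = 26.6, about 27 working days.
- If only the question 6 count were costed, the figure would be 2 days in either language. Question 7 would then add no overstatement, and the loss would be the missing answers to questions 9 to 11.

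For this patient the overstatement is therefore anywhere from 0 to about 27 working days, depending on a costing rule the protocol does not give.

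**Question 6.** A five-day worker absent throughout the window has 4 × 5 = 20 working days of absence. If the French note were read as calendar days of sick leave, the entry could reach 28, and 28/20 = 1.40. That is an upper bound on a possible reading.

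**The case against.** The strongest reply is that French question 7, read in sequence, means the right thing. It follows a question about recent absence, is limited to a complete uninterrupted period, and leads to a question about the start of one leave. A careful reader with an isolated recent sick day could take it to ask whether that absence began before the window, and would answer no. This has force for patient B, whose misrouting is possible but not certain. It does not help patient C.

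The English form is not perfectly clean either. It can be read as any unbroken absence of more than 4 weeks, which would let a patient off work to day 50 answer yes. This weakens the contrast for long early leaves but does not remove it. For example, a leave from day 50 to day 70 lasts 20 days, fewer than 28, so English gives no on either reading while French gives yes. The text at hand does not show Dutch questions 7 to 11, so the Dutch cannot settle the intended meaning here.

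A reader might infer that any recent sick day routes a French-speaking patient as continuously absent since the stroke. The document does not support that. A sick day leads only to question 7, a yes is still needed, and question 8 takes whatever date the patient enters. Nor is it right to set 64 days against the 2 days at question 6: the first covers 90 days and the second 4 weeks, and the 64 assumes a costing rule that is not stated. The calendar-day reading of French question 6 is possible but not shown, since the preceding question asks for working days per week.

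It is also fair that the reach is small. Randomization is stratified by center (section 8.2), so language should be roughly balanced between arms.

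**Conclusion.** The point stands as a wording mismatch with a data consequence. French question 7 does not ask what English question 7 asks, and its answer determines whether reduced output at work is recorded. Patients whose leave began before the window and ended inside it are misrouted if they follow the French form as written, taking the English to mean absence through the window. Those who returned earlier and then had a separate sick day may be. Patients still continuously off work, or with no sick day in the window, are unaffected.

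The effect is confined to employed French-language respondents, whose number is not given, and to productivity costs within the tertiary economic objective. The primary endpoint, sample size and error rates are untouched. The effect on the cost result cannot be computed, because neither that number nor a costing rule for question 8 is stated; such a rule may stand in an analysis plan that is not shown. The 0 to 27 working days above describe one assumed patient and do not estimate the trial-level effect. The difference at question 6 is a secondary matter of clarity.

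**What to change.** 1. Reword French question 7 so that it asks about an uninterrupted sickness absence lasting longer than the entire 4-week period, as in English. Check the new wording against Dutch question 7 before release.
2. Align the French note at question 6 with the English and Dutch, so that only working days are counted.
3. For French forms already returned, flag for checking any with yes at question 7 but fewer days at question 6 than the patient's usual working days in 4 weeks (4 × the answer to question 5). Treat questions 9 to 11 as missing in those forms. Do not reclassify automatically. The flag should be *fewer than*, not *different from*, because a fully absent five-day worker who counted calendar days might enter 28 rather than 20 and would be wrongly rejected by an equality rule. The flag cannot restore answers that were never asked.

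The cost is two sentences in one language version, one consistency check and a small amendment to a patient-facing form, with no new assessment. It is best done early, since each form completed before the correction may lose answers for good.

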**Question 8. Quand votre congé maladie a-t-il débuté ?**

Jour/mois/année : ..../..../.....

Passez à la question 12. *Veillez d'abord lire l'explication précédant la question 12.*

**Question 9. Au cours des 4 dernières semaines, y a-t-il eu des jours où vous avez été gêné(e) au travail par des problèmes physiques ou psychologiques ?**

- Non  
 Oui

Vous avez répondu « Oui » ? Passez aux questions 10 et 11.

Sinon, passez à la question 12. *Veillez d'abord lire l'explication précédant la question 12.*

**Question 10. Pendant combien de jours avez-vous été gêné(e) par des problèmes physiques ou psychologiques lorsque vous étiez au travail ? (Comptez uniquement les jours où vous avez travaillé au cours des 4 dernières semaines.)**

..... jours de travail

**Question 11. Les jours où vous avez été gêné(e) par ces problèmes, avez-vous eu des difficultés à accomplir la même charge de travail que d'habitude ? Ces jours-là, quelle charge de travail avez-vous pu réaliser en moyenne ?** Observez les chiffres ci-dessous. Un 10 signifie que vous avez été capable d'accomplir la même charge de travail que d'habitude. Un 0 signifie que vous n'avez été capable de réaliser aucune tâche ces jours-là. Entourez le chiffre qui correspond le mieux à votre cas.

Ces jours-là,  
je n'ai rien  
pu faire du  
tout.

J'ai pu accomplir  
la même charge  
de travail que  
d'habitude

J'ai pu  
accomplir la  
moitié du  
travail habituel.

0    1    2    3    4    5    6    7    8    9    10

**Explication à la question 12**

Même dans le cadre d'un travail non rémunéré, vous pouvez souffrir de problèmes physiques ou psychologiques. Parfois, vous pouvez avoir plus de difficultés à effectuer certaines activités quotidiennes. Vous avez par exemple du mal à vous occuper de vos enfants ou à faire du bénévolat. Ou bien vous n'êtes pas capable d'aller faire vos courses ou de jardiner. Les questions suivantes portent sur cela.

**Question 12. Y a-t-il eu certains jours où vous avez été contraint(e) de réaliser moins de travail non rémunéré à cause de problèmes physiques ou psychologiques ?** Cela concerne uniquement les quatre dernières semaines.

- Non
- Oui

Vous avez répondu « Oui » ? Passez aux questions 13 et 14.

Sinon, c'était la dernière question.

**Question 13. Combien de jours cela vous est-il arrivé ?** Comptez uniquement les jours inclus dans les 4 dernières semaines.

..... jours

**Question 14. Imaginez que quelqu'un, votre compagne/compagnon, un membre de votre famille ou un ami par exemple, vous ait aidé ces jours-là et qu'il ou elle ait accompli pour vous tout le travail non rémunéré que vous n'avez pas été capable d'effectuer. Combien d'heures en moyenne cette personne a-t-elle passé à réaliser ces tâches ces jours-là ?**

..... heures en moyenne ces jours-là

**C'était la dernière question de ce formulaire.**

**Avez-vous des questions ou des commentaires à formuler ?**

Vous avez peut-être des questions ou des commentaires à formuler ?

Veuillez les écrire ci-dessous.

.....  
.....

**Merci!**

## Vragenlijst over uw zorggebruik

Onderzoekers noemen deze vragenlijst de iMTA MCQ (iMCQ).

### **Toelichting**

#### **Lees dit alstublieft eerst!**

#### **Kunt u de lijst niet zelf invullen?**

Als u de lijst niet zelf kunt invullen, kan iemand u misschien helpen. Bijvoorbeeld een familielid.

#### **Waar gaat de vragenlijst over?**

De vragenlijst gaat over uw zorggebruik in de afgelopen 3 maanden.

#### **Hoe lang duurt het om de lijst in te vullen?**

Het duurt ongeveer 20 minuten om de lijst in te vullen.

#### **Hoe moet u de vragenlijst invullen?**

Begin bij de eerste vraag en volg de nummering.

- Bij sommige vragen kunt u tekst of een getal invullen, bij andere vragen kunt u een hokje/optie aanklikken
- U kunt geen foute antwoorden geven.

#### **Wat gebeurt er met uw antwoorden?**

Uw antwoorden worden gebruikt voor onderzoek. Alleen de onderzoekers zien uw antwoorden. Dus niemand anders.

De onderzoekers schrijven uw naam nergens op. En zij vertellen aan niemand dat u aan het onderzoek heeft meegewerkt.

#### **Fijn dat u de lijst voor ons wilt invullen!**

## Vragen over zorggebruik

### Toelichting

Wij willen graag weten met welke dokters u in de afgelopen 3 maanden een afspraak had. Het gaat om afspraken voor uzelf. Ook andere zorgverleners tellen mee.

Bijvoorbeeld de fysiotherapeut.

Welke afspraken tellen mee?

- Controles
- Afspraken omdat u een lichamelijke of psychische klacht had
- Afspraken waarbij de dokter bij u thuis kwam
- Telefonische afspraken
- Telefoontjes met de receptenlijn

Wat telt niet mee?

- Afspraken voor een ander, bijvoorbeeld voor uw kind
- Telefoontjes om een afspraak te maken

Weet u niet precies hoeveel afspraken het waren? Schrijf dan op hoeveel het er ongeveer waren.

**Vraag 1a. Heeft u in de afgelopen 3 maanden afspraken gehad met uw huisarts?**

- Nee  
 Ja

Heeft u "Ja" aangekruist? Beantwoord dan vraag 1b.  
Ga anders verder met vraag 2.

**Vraag 1b. Hoeveel afspraken had u in de afgelopen 3 maanden met uw huisarts?**

- ..... afspraken met de huisarts

**Vraag 2. Hoeveel afspraken had u in de afgelopen 3 maanden met een fysiotherapeut? Of met een caesartherapeut, therapeut mensendieck of een manueel therapeut?** Tel alle afspraken met deze therapeuten bij elkaar op.

- Geen enkele afspraak  
 ..... afspraken

**Vraag 3. Hoeveel afspraken had u in de afgelopen 3 maanden met een ergotherapeut?**

- Geen enkele afspraak  
 ..... afspraken

**Vraag 4. Hoeveel afspraken had u in de afgelopen 3 maanden met een logopedist?**

- Geen enkele afspraak  
 ..... afspraken

**Vraag 5. Hoeveel afspraken had u in de afgelopen 3 maanden met een psycholoog? Of met een psychotherapeut of psychiater?** Tel alle afspraken met deze zorgverleners bij elkaar op.

- Geen enkele afspraak  
 ..... afspraken

**Vraag 6a. Heeft u in de afgelopen 3 maanden hulp van de thuiszorg gehad?**

- Nee  
 Ja

Heeft u “Ja” aangekruist? Beantwoord dan vraag 6b-6d.  
Ga anders verder met vraag 7a.

**Vraag 6b. Wat voor hulp van de thuiszorg heeft u gehad in de afgelopen 3 maanden?**

U kunt meer dan 1 hokje aankruisen.

- Huishoudelijke hulp  
voorbeeld: stofzuigen, bed opmaken, boodschappen doen
- Verzorging van uzelf  
voorbeeld: hulp bij douchen of aankleden
- Verpleging  
voorbeeld: verband omdoen, medicijnen geven, bloeddruk meten

**Vraag 6c. Hoeveel weken heeft u deze thuiszorg gehad?** Tel alle weken in de afgelopen 3 maanden bij elkaar op. *Let op: een periode van 3 maanden telt 13 weken.*  
Huishoudelijke hulp: .... weken in de afgelopen 3 maanden

Verzorging van uzelf: .... weken in de afgelopen 3 maanden

Verpleging: .... weken in de afgelopen 3 maanden

**Vraag 6d. Hoeveel uur thuiszorg kreeg u in deze weken gemiddeld?**

Huishoudelijke hulp: gemiddeld ... uur in de week

Verzorging van uzelf: gemiddeld ... uur in de week

Verpleging: gemiddeld ... uur in de week

**Vraag 7a. Heeft u in de afgelopen 3 maanden bloedverdunners\*, gebruikt?**

- Nee  
 Ja

\* carbasalaatcalcium (ascal, acetylsalicylzuur), clopidogrel (plavix, grepid, iscover), prasugrel (efient), ticagrelor (brilique), dipyidamol (persantin), acenocoumarol (sintrom), fenprocoumon (marcoumar), dabigatran (pradaxa), rivaroxaban (xarelto), apixaban (eliquis), edoxaban (lixiana)

Heeft u “Ja” aangekruist? Vul dan bij vraag 7b in welke medicijnen en hoeveel.  
Ga anders verder met vraag 8.

